Title: Efficacy of four local anesthesia protocols for mandibular first molars with symptomatic irreversible pulpitis. A randomized clinical trial

NCT number: NCT04929522

Date: 5-October- 2021

Subjects and methods

Ethical considerations

This trial was conducted with the approval of the institutional review of board (IRB) of the ethics committee at the Faculty of Dentistry, Ain Shams University, Cairo, Egypt (FDASU-REC772019). The protocol was registered at the clinical trials website (<http://www.clinicaltrials.gov>, ID: NCT04929522). Subjects were treated in full compliance with the World Medical Association Declaration of Helsinki (2008).

Trial design

This study was designed as a prospective, parallel, triple blinded, and randomized clinical trial with an allocation ratio of 1:1. The trial design is being reported according to the Preferred Reporting Items for Randomized Trials in Endodontics (PRIRATE) 2020 guidelines (Nagendrababu *et al.* 2020).

Sample size calculation

A sample size calculation was performed based on the study by Kanaa *et al.* (2012). This research was based on a type I error of 0.05 and a power of 0.8 and indicated that ideally, a sample size of 36 in each group would be required to detect a 20% difference in the success rate of the test groups. To increase the validity of the study, 40 subjects in each group were considered.

Eligibility criteria

Patients who participated in this trial were allocated from the outpatient emergency clinic of the Endodontic Department, Faculty of Dentistry, Ain Shams University in Cairo, Egypt, between January 1st, 2021, and May 30th, 2021. All the patients were informed about the benefits, risks, and indications for endodontic treatment and possible adverse effects of the proposed interventions. All the included patients signed a written informed consent.

Inclusion criteria

Patients included in the study were healthy males and females (Category: American Society of Anesthesiologists class 1) aged 21-49 years, with no physical disability, facial paresthesia, or psychological problems, presenting with a mandibular first molar, with signs and/or symptoms of symptomatic irreversible pulpitis.

Exclusion criteria

Pregnant women, patients who took analgesics or other medications that would alter the inflammatory response of the pulp or provide analgesia 12- hours pre-operatively, those with known sensitivity to the pharmaceuticals used in this trial were excluded from the study. Also, those with pathological periodontal pockets more than 3 mm depth at the injection site were excluded.

Randomization and blinding

Participants were allocated randomly into four groups with 1:1 allocation ratio to ensure random selection by using computer-generated randomization (www.randome.org). The sequence was therefore generated.

Allocation concealment mechanism: The sequentially generated numbers were placed in opaque envelopes until the intervention was conducted. Each participant was asked to select an envelope that determines which group of intervention was assumed.

Implementation: The co-researcher used computer-generated randomization for participants who achieve eligibility criteria. Accordingly, participants were enrolled in either of the groups under study. The participants, the operator who initiated endodontic treatment, monitored the pain and heart rate, and the statistician were blinded to the anesthetic techniques.

Intervention

The diagnosis was confirmed through history reporting spontaneous pain, a moderate to a severe painful response that persists after thermal stimulation, a prolonged response to cold testing with Endo-Ice (1,1,1,2 Tetrafluoroethane; Hygenic Corp, Akron, OH), absence of percussion sensitivity, and the periapical aspect of the tooth in the bidimensional periapical radiograph was normal. Matching vital contralateral teeth were also tested to ensure an accurate diagnosis and to serve as controls. To prevent bias, this diagnostic step was performed by one investigator (AH). In contrast, another investigator (DK) was responsible for administering all anesthetic injections. A third investigator (SS) was responsible for root canal treatment procedures, pain recording and monitoring of heart rate. All investigators have a minimum of 12 years of clinical experience in endodontics.

One hundred and eighty-five patients consecutively visited were assessed for eligibility. Twenty-five patients were excluded for different reasons, and the others 160 (eighty-four female and seventy-six male patients) were allocated to the trial and randomly assigned into four groups (n=40) as follows (Figure 1):

Group 1 (IANB): After determining the injection site and aspiration, 3.6ml of the anesthetic solution was administered using the standard inferior alveolar nerve block (IANB) injection. This was considered the control group.

Group 2 (IANB + IO): A standard IANB was administered using 1 carpule (1.8 ml) of the anesthetic solution followed by another carpule (1.8 ml) using the supplemental intraosseous infusion (IO) injection with the Anesto system (W&H Dentalwerk Bürmoos, Austria). To ensure comfort during the procedure, 0.1ml of the anesthetic solution was infiltrated at the perforation site using the standard syringe. The perforation site was selected near the junction of the attached and unattached gingival tissues, immediately distal to the first molar. Perforation was accomplished by operating the Anesto handpiece at full speed, with constant moderate pressure maintained until the perforator was felt to 'drop' into the cancellous bone. The anesthetic solution was then deposited over 60 seconds. The Anesto handpiece was again retracted and, with the perforator rotating, removed from the injection site. **Group3(IANB+PDL):**A standard IANB was administered using 1 carpule (1.8ml) of the anesthetic solution, followed by another carpule (1.8 ml) using the supplemental periodontal ligament (PDL) injection. The needle was wedged with force into the PDL space between the tooth and the alveolar

crest of the bone, at 30-degrees to the long axis of the tooth. The thumb and index fingers of the left hand supported the needle to prevent buckling. The handle of the syringe was squeezed firmly until backpressure was achieved. The anesthetic solution was injected mesially and distally to the treated molar.

Group 4 (IANB + BI): A standard IANB was administered using 1 carpule (1.8 ml) of the anesthetic solution, followed by another carpule (1.8 ml) using the supplemental buccal infiltration at the buccal side of the affected tooth. The anesthetic solution was injected halfway to the mesiodistal width of the clinical crown.

IANB, PDL, and BI injections were performed with a conventional aspirating dental syringe (Patterson Dental Co, Montana, USA) and a 27-G needle at a rate of 1.8 mL/min. The anesthetic solution used for all techniques was Articaine HCL 4% with 1:100,000 adrenaline (Artinibsa, Inibsa, Barcelona, Spain).

Outcome assessment

Anesthesia was confirmed 15 minutes post-injection by the following responses: (1) confirmation of lip numbness, (2) negative response to Endo-Ice, (3) negative response to the maximum output of the electric pulp tester (Parkell, Edgewood, NY, USA). Root canal treatment procedure was later initiated. The patients were asked to rate their pain score once using a verbal rating scale (VRS) from 0 to 3. The pain was scored as follows: Score 0, no pain; Score 1, mild pain; Score 2, moderate pain; or Score 3, severe pain. After rubber dam placement and during caries removal, access preparation, and pulpectomy, the success of the anesthetic technique was determined by VRS. The technique was considered as a 'success' when the patient reported no pain (VRS = 0 or 1) and as a 'failure' otherwise (VRS >1).

Heart rate changes were monitored with a finger pulse oximeter (Medlinket, Shenzhen Med-link Electronics, Shenzhen, China). It was recorded from 2 min before to 5 min after injection, at 30-s intervals.

Statistical analysis

All analyses were undertaken with IBM SPSS Statistics (SPSS 26.0; SPSS Inc., Chicago, IL). The anesthetic success rates were analyzed using the chi-square test. Age differences were analyzed using One Way ANOVA; gender differences were analyzed using the Fischer Exact test, while heart rate changes were analyzed with the Kruskal Wallis test, being non-normally distributed. Statistically significant differences were set at the $P < 0.05$ level.

Results

Every tested contralateral teeth used as control, responded positively to the thermal and electrical pulp testing during the diagnostic phase. All the participants had a positive lip sign (numbness) and a negative response to thermal and electrical testing 15 minutes post-injection of all techniques and 100% of the anaesthetic block was considered effective. No supplemental anaesthetic infiltration was administrated. No paresthesia or adverse effects associated with the use of Articaine IANBs were found in this trial.

Table 1. shows the distribution of the participants. There were no differences in the success rate related to the age or gender ($P > 0.05$) so the participants were homogenously distributed among the study groups.

Table 2 represents the anesthetic efficacy of the different tested injection protocols. IANB +IO injection had a statistically higher success rate 92.5% ($p > 0.05$), followed by IANB + PDL injection (72.5%), IANB + BI injection (65.0%), respectively with no statistical differences between them ($p < 0.05$). In comparison, IANB injection alone had a success rate of (40%) which was statistically the lowest compared to other techniques ($p > 0.05$).

An increase in the heart rate was noted in patients who received IANB + IO injection, and this was statistically significant compared to the other injection techniques ($p > 0.01$). Differences in heart rate changes among the other injection technique were non-significant ($P < 0.05$). Relative risk values are reported in Table 2. The relative risk for all the supplemental anaesthesia techniques was less than 1 indicating that the risk of the outcome (high VRS numbers) was decreased by using supplemental anaesthesia protocol. The actual difference in the observed risk of events between the experimental and IANB (Control) techniques is shown in Table 2. The risk in the intervention group was decreased between 25 and 52% by using supplemental anaesthesia.

Table 1. Demographic data of the patients for each anaesthetic group.

	IANB n = 40	IANB+IO n = 40	IANB+PDL n = 40	IANB+BI n = 40	P-value
Gender n (%)					
Female	25 (62.5%)	28 (70%)	26 (65%)	23(57.5%)	0.740
Male	15 (37.5%)	12 (30%)	14 (35%)	17 (42.5%)	
Age (Mean \pm SD)	29 \pm 9.1	31 \pm 6.8	33 \pm 5.5	29 \pm 8.2	0.055

Table 2: Success and failure rates for the four local anaesthesia protocols.

Group	Success n(%)	Failure n(%)	OR [95% CI]	Relative risk [95% CI]	Risk difference
IANB (control)	16(40%) ^a	24(60%)	---	---	---
IANB +IO	37(92.5%) ^c	3(7.5%)	0.05[0.01-0.21]	0.13[0.04-0.38]	-0.52
IANB + PDL	29(72.5%) ^b	11(27.5%)	0.25[0.10-0.65]	0.46[0.26-0.81]	-0.32
IANB + BI	26(65.0%) ^b	14(35.0%)	0.36[0.15-0.89]	0.58[0.36-0.95]	-0.25

Different superscript letters indicate a statistically significant difference within the same vertical column ($p > 0.05$)

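### Does calling VRS 0 or 1 'no pain', and leaving unsaid what the single pain rating covers, undermine the success endpoint?

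*Combined protocol and SAP*

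**What the plan says.** All the relevant text on the rule is in the Outcome assessment section.

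- Scale: "Score 0, no pain; Score 1, mild pain; Score 2, moderate pain; or Score 3, severe pain".
- Success: the technique succeeds "when the patient reported no pain (VRS = 0 or 1".
- Failure: "and as a 'failure' otherwise (VRS >1".
- Number of ratings: "The patients were asked to rate their pain score once using a verbal rating scale (VRS) from 0 to 3".
- Period judged: "during caries removal, access preparation, and pulpectomy, the success of the anesthetic technique was determined by VRS".

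The Statistical analysis section compares success rates by a chi-square test. The Results section describes the adverse outcome when it interprets the relative risks: "the risk of the outcome (high VRS numbers) was decreased by using supplemental anaesthesia protocol". Table 2 gives success and failure counts for four arms of 40, with no breakdown by individual score.

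**The concern.** There are two separate points.

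First, a patient who scores 1 has, by the document's own scale, mild pain, but the success definition describes that patient as having none. A reader who takes the words and skips the parenthesis would read 92.5% success for the block plus intraosseous injection as 92.5% of patients free of pain. The document reports no pain-free rate for any arm.

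Second, one rating is set against three steps. If it was taken early, pain during pulpectomy would be missed and success overstated. If it was an overall or worst score, nothing would be missed. The document does not state which.

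This is the only efficacy endpoint, and everything in Table 2 rests on it. A real uncertainty over what was counted would therefore reach every efficacy conclusion.

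**Working it through.** **The label.** Compare two readings of the rule.

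| VRS score | Scale meaning | By the numbers (0 or 1 succeeds, above 1 fails) | By the words alone (only no pain succeeds) |
|---|---|---|---|
| 0 | none | success | success |
| 1 | mild | success | not a success, yet not above 1 |
| 2 | moderate | failure | failure |
| 3 | severe | failure | failure |

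The numerical reading assigns each of the four scores exactly once and conflicts only with the two-word gloss. The verbal reading contradicts the parenthesis after success and also the one after failure, and it leaves a score of 1 with no consistent class. The Results text, which equates the adverse outcome with high scores, fits the numerical reading.

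**Whether any figure depends on the label.** The inputs are the Table 2 counts (success, failure): control 16, 24; intraosseous (IO) 37, 3; periodontal ligament (PDL) 29, 11; buccal infiltration (BI) 26, 14. Each pair adds to 40, so every patient was classified. For failure, with f failures and s successes in a supplemental arm:

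- relative risk = (f/40) / (24/40) = f/24
- odds ratio = (f × 16) / (s × 24)
- risk difference = f/40 − 24/40

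| Arm | Relative risk (printed) | Odds ratio (printed) | Risk difference (printed) |
|---|---|---|---|
| IO | 3/24 = 0.125 (0.13) | 48/888 = 0.054 (0.05) | 0.075 − 0.600 = −0.525 (−0.52) |
| PDL | 11/24 = 0.458 (0.46) | 176/696 = 0.253 (0.25) | 0.275 − 0.600 = −0.325 (−0.32) |
| BI | 14/24 = 0.583 (0.58) | 224/624 = 0.359 (0.36) | 0.350 − 0.600 = −0.250 (−0.25) |

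All agree to rounding. Wald intervals on the log scale also match the printed ones; for IO the relative risk interval is 0.041 to 0.382, against a printed 0.04 to 0.38. The counts are the only inputs. Rewording the gloss as *no or mild pain* changes none of them.

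**The single rating.** Three readings can be tested against the two sentences.

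1. One overall or worst score covering the three steps: consistent with a single rating and with all three steps being named.
2. One score at an early step only: consistent with a single rating, but hard to square with success being judged during pulpectomy as well.
3. A score at each step: consistent with the three steps, but contradicts a single rating.

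Only the first satisfies both sentences. In addition, the Intervention section gives root canal treatment and pain recording to one investigator, and the Randomization and blinding section describes that operator as blinded to technique. Whatever convention was used, the same person recorded the scores in all four arms. That argues against arm-by-arm differences in recording. It would not by itself rule out an effect if one technique wore off sooner and the score had been taken early.

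**The case for a change.** The strongest opposing case is that an endpoint should be reproducible from its text, and this one is not fully so: the words are wrong, and another team could not tell whether to record an overall or a worst score. Its supporters can add that conclusions might differ for a pain-free endpoint. On unadjusted Pearson tests, IO against PDL has P = 0.019 and BI against control P = 0.025 with the reported counts. If 10% of successes in every arm had scored 1 and were recounted as failures, these would become 0.066 and 0.044; at 25%, 0.167 and 0.086.

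The arithmetic is correct, but it answers a different question. Those P values belong to an endpoint of score 0 only, which the numerical rule does not define. The 10% and 25% shares have no source in the document, nor does the assumption that they are equal across arms. Pain-free counts could lie anywhere from 0 up to the printed 16, 37, 29 and 26. None of this measures the effect of a wrong word beside a correct cut-off, and none of it bears on the timing of the rating.

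What stands is modest. The gloss is inaccurate, and a clause saying what the rating summarises would have helped. Score-by-score counts would be informative, but they are optional reporting. Scoring each step and taking the worst is a reasonable design preference, but it is out of reach here: the Eligibility criteria section places recruitment "between January 1st, 2021, and May 30th, 2021", and the document is dated 5 October 2021.

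**Conclusion.** No change follows. The label is a clerical slip next to an explicit and exhaustive numerical rule; its effect on every count, estimate and test is zero, and Table 2 success should be read as no or mild pain. The coverage of the single rating is a gap with one natural reading, a score spanning the three steps, under which no pain is missed. An early rating would overstate success to an unknown degree, but the text fits that reading poorly, and no effect on the comparison between arms is shown in either direction.

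This rests on two assumptions: that the counts were made by the stated 0-or-1 rule, which nothing in the document contradicts, and that the one rating covered the period the document names.

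### As described, the procedures do not support the claim that the operator who records pain was blinded: the heart-rate schedule given to that same person spans the injections

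*Combined protocol and SAP*

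**What the plan says.** All places are in the combined protocol and SAP.

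- **Trial design** calls the study a "prospective, parallel, triple blinded, and randomized clinical trial with an allocation ratio of 1:1".
- **Randomization and blinding** lists the blinded parties as the participants and "the operator who initiated endodontic treatment, monitored the pain and heart rate, and the statistician were blinded to the anesthetic techniques".
- **Intervention** divides the work among three investigators. One makes the diagnosis. A second "was responsible for administering all anesthetic injections". The third "was responsible for root canal treatment procedures, pain recording and monitoring of heart rate".
- **Outcome assessment** names the device ("Heart rate changes were monitored with a finger pulse oximeter") and the schedule: "It was recorded from 2 min before to 5 min after injection, at 30-s intervals".
- **Intervention, Groups 1 to 4** describes a nerve block alone (IANB), or a block followed by intraosseous (IO), periodontal ligament (PDL) or buccal (BI) injection. For the IO arm, "Perforation was accomplished by operating the Anesto handpiece at full speed". No sham supplemental injection is described for the control arm.
- **Outcome assessment** also defines success as a patient-rated VRS of 0 or 1 on a 0 to 3 scale.

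**The concern.** Separating the injector from the operator protects the outcome only if the operator does not learn which technique was used. Making the operator responsible for heart rate over a period that includes the injections undoes that separation. The text would leave more room if it did not say who monitored heart rate. It does say, and it names the person who later records pain.

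That person then treats the tooth, asks for the pain rating and writes it down. Success turns on the line between mild (1) and moderate (2). How the question is put, how firmly the operator proceeds and how a hesitant answer is recorded could all reflect knowledge of the arm. No outcome is labelled primary, but VRS success rate is the one on which the sample size rests. With no sham, participants may also recognise their technique, so operator blinding carries more of the weight.

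**Working it through.** **1. Do the readings overlap the injections?**

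Inputs (Intervention and Outcome assessment): 3.6 ml in total per arm, as 3.6 ml or 1.8 + 1.8 ml; 1.8 mL/min for IANB, PDL and BI; IO deposited over 60 s; a reading every 30 s from −120 s to +300 s.

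- Delivery time = volume / rate. IANB, PDL and BI arms: 3.6 / 1.8 = 2 min = 120 s.
- IO arm: 1.8 / 1.8 = 1 min for the block, plus 1 min for the IO = 120 s. The preliminary infiltration and the perforation are not timed, so this is a minimum.
- If both limits count from the start of injection: (120 + 300) / 30 + 1 = 15 readings, of which 120 / 30 + 1 = 5 (at 0, 30, 60, 90 and 120 s) fall during delivery.
- If the 5 minutes count from the end of injection: (120 + 120 + 300) / 30 + 1 = 19 readings, with the same 5 during delivery.

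On either count the monitor is engaged before, during and after the injections.

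**2. Can the techniques be told apart?**

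The four are a block alone, a motor-driven bone perforator, a needle wedged into the ligament mesially and distally, and an injection on the buccal side. Someone watching could distinguish them. The section names the oximeter's maker but describes nothing that would hide the technique from the person monitoring heart rate.

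**3. How sensitive are the results?**

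Table 2 reproduces for BI: 26/40 = 65.0% against 16/40 = 40%; risk difference 14/40 − 24/40 = −0.25; relative risk 0.35/0.60 = 0.58. The document prints no pairwise p-values, so those below are recalculated as Pearson chi-square, unadjusted and without continuity correction. With 40 per arm, successes a and c, S = a + c and F = 80 − S:

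χ² = 80(a − c)² / (S × F), 1 df, 5% critical value 3.84.

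| Contrast | Counts | χ² | p |
|---|---|---|---|
| BI v IANB, as reported | 26 v 16 | 80×100/(42×38) = 5.01 | 0.025 |
| one patient moved in each arm | 25 v 17 | 80×64/(42×38) = 3.21 | 0.073 |
| one patient moved in BI only | 25 v 16 | 80×81/(41×39) = 4.05 | 0.044 |
| PDL v IANB, as reported | 29 v 16 | 80×169/(45×35) = 8.58 | 0.003 |
| IO v IANB, as reported | 37 v 16 | 80×441/(53×27) = 24.65 | <0.001 |

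With control held at 16, significance is kept at 25 successes (p=0.044) and lost at 24: 80×64/(40×40) = 3.20, p=0.074. The one-arm changes from success to failure needed are therefore 26 − 24 = 2 for BI, 29 − 24 = 5 for PDL and 37 − 24 = 13 for IO.

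**The case against.** **Presence is inferred.** The heart-rate sentence is passive, and being responsible for monitoring need not mean watching the display at the chair. A screen, a remote display, stored readings or a second recorder could have kept the operator blind. This stands as a limit on wording: it cannot be said that the operator was certainly unblinded. It does not remove the conflict, because the documents assign the task, set the schedule and describe no such measure.

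**The patient supplies the score.** Patients choose among labelled categories and the cutoff is fixed, so the operator does not grade pain. This stands too. It narrows the route for bias to elicitation, recording and conduct of the procedure. The documents contain no evidence that bias occurred.

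**The main contrasts are not fragile.** IO and PDL against control tolerate far more reclassification than BI does, and the overall four-arm chi-square is 25.8 on 3 df (p≈0.00001). Fragility near p=0.05 is also a small-sample property and does not measure assessor bias. Both points stand.

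**A reader might infer that IO v PDL is also exposed**, since 37 v 29 gives p=0.019 and 36 v 30 gives p=0.078. The documents do not support using it here. Both arms are supplemental, so a leaning toward supplemental techniques would not push them apart; that would need a bias for IO and against PDL, for which there is no basis.

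**Conclusion.** The point holds for the procedures as described. The division of roles and the heart-rate window together leave the stated operator blinding, and so the triple-blind label, without support. This rests on one inference: that a finger device read every 30 seconds by the responsible investigator puts that person where the technique can be seen or heard.

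The effect on the results cannot be estimated. If bias favoured the supplemental techniques, BI v IANB is the conclusion most exposed: one reclassified patient in each arm, or two in the BI arm, removes significance, though one change in one arm does not. PDL v IANB and IO v IANB need 5 and 13 one-arm changes.

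A reader might go further and conclude that the operator could not possibly have been blinded, or that the efficacy findings are invalid. The documents support neither. They leave the means of blinding unexplained, and they show neither that unblinding happened nor that any score was altered.

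**What to change.** **For a trial still to be run on this plan:** assign heart-rate reading in the window to an existing investigator who does not record pain, for example the one who made the diagnosis, or take it from the oximeter's record if the device keeps one (the documents do not say). Have the treating and pain-recording investigator enter only after the window closes. If the window and the 15-minute anaesthesia check count from the same point, 15 − 5 = 10 minutes remain before that check. The plan should also say who performs the check, which it does not do now. The cost is extra time per patient for the diagnosing investigator; no added staff or procedure is needed.

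**For the trial as reported:** state who took the readings, from where, and how technique was hidden. If it was run as written, remove the operator/pain recorder from the list of blinded parties, withdraw the triple-blind label, and report VRS success as recorded by an unblinded assessor. This changes no count or test; the cost is a less favourable description of the design.

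Neither change repairs participant blinding. With no sham described, patients, who supply the score, may still recognise their technique, and the report should say so.

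### The success-rate analysis names a chi-square test at 0.05 but no comparison family or multiplicity control, although all six pairs are decided; two of the five claimed differences are borderline and depend on the unstated method

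*Combined protocol and SAP*

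**What the plan says.** The Statistical analysis section gives one sentence on the success rates, "The anesthetic success rates were analyzed using the chi-square test", and one on the threshold: "Statistically significant differences were set at the $P < 0.05$ level". It does not say how pairs of groups are compared, which pairs form the family, or whether any adjustment is made. No other section does.

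The design has four arms ("Participants were allocated randomly into four groups with 1:1 allocation ratio"), so six pairs are possible. Of the IANB-alone arm, the Intervention section says "This was considered the control group", and every odds ratio, relative risk and risk difference in Table 2 is against that arm.

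The Results make statements about all six pairs:

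- IO against the rest: "IANB +IO injection had a statistically higher success rate 92.5" (per cent).
- PDL and BI: "respectively with no statistical differences between them".
- IANB alone: "which was statistically the lowest compared to other techniques".

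Table 2 encodes the same decisions as letters: a for IANB, c for IO, b for PDL and b for BI. By its footnote, groups with different letters differ significantly. No pairwise p-value is given, only inequalities. Their signs run opposite to the wording; I follow the wording and the letters, and treat the signs as a separate reporting matter.

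**The concern.** A single four-arm chi-square test can show that the arms are not all alike. It cannot assign letters or order the arms in tiers; that needs a pairwise procedure, and none is named. If each pair was tested at 0.05 without adjustment, then 0.05 is the error rate of one comparison and not of the three-tier ranking.

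Two claims are at stake. IO v PDL separates the top tier from the middle one. BI v IANB is needed for the statement that the control arm is below every other technique. The plan also leaves open whether the family is the three comparisons with control or all six pairs, and the answer affects both claims.

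**Working it through.** **Inputs.** Table 2, successes out of 40: IANB 16, IO 37, PDL 29, BI 26. Threshold 0.05 from the Statistical analysis section.

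**Overall test.** The mean count is 108/4 = 27 and the pooled rate is 108/160 = 0.675. Pearson χ² = (11² + 10² + 2² + 1²) / (40 × 0.675 × 0.325) = 226 / 8.775 = 25.75 on 3 df, p = 0.00001.

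**Reproducing the letters.** For two arms of 40 with success counts x₁ and x₂, S total successes and F total failures, Pearson χ² = 80(x₁ − x₂)² / (S × F) on 1 df. Holm orders the six p-values, multiplies them by 6, 5, 4, 3, 2 and 1, and does not let an adjusted value fall below the one before it.

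| Pair | χ² | Raw p | Holm multiplier | Holm p | Table 2 letters |
|---|---|---|---|---|---|
| IO v IANB | 80 × 21² / (53 × 27) = 24.65 | 0.0000007 | 6 | 0.000004 | differ |
| IO v BI | 80 × 11² / (63 × 17) = 9.04 | 0.0026 | 5 | 0.0132 | differ |
| PDL v IANB | 80 × 13² / (45 × 35) = 8.58 | 0.0034 | 4 | 0.0136 | differ |
| IO v PDL | 80 × 8² / (66 × 14) = 5.54 | 0.0186 | 3 | 0.0557 | differ |
| BI v IANB | 80 × 10² / (42 × 38) = 5.01 | 0.0252 | 2 | 0.0557 | differ |
| PDL v BI | 80 × 3² / (55 × 25) = 0.52 | 0.469 | 1 | 0.469 | same |

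For BI v IANB, 2 × 0.0252 = 0.0503, raised to the preceding 0.0557. The raw column gives exactly the printed letters; Yates-corrected and Fisher tests give the same six decisions at 0.05. The Holm column does not: five significant pairs become three.

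**How far the two losses depend on method.**

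| Method | IO v PDL | BI v IANB |
|---|---|---|
| Six pairs, Hochberg, Pearson | 0.0503 | 0.0503 |
| Six pairs, Bonferroni, Pearson | 0.111 | 0.151 |
| Six pairs, Holm, Fisher | 0.110 | 0.110 |
| Six pairs, Holm, Yates | 0.118 | 0.118 |
| Six pairs, Hommel, Pearson | 0.038 | 0.0503 |
| Six pairs, Holm, likelihood-ratio | 0.047 | 0.049 |
| Six pairs, closed Pearson test | 0.019 | 0.025 |
| Six pairs, Benjamini-Hochberg, Pearson (false discovery rate only) | 0.028 | 0.030 |
| Three control pairs, Holm, Pearson | outside family | 0.025 |
| Three control pairs, Bonferroni, Pearson | outside family | 0.075 |

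Holm over the three control comparisons gives 3 × 0.0000007 = 0.000002 (IO), 2 × 0.0034 = 0.007 (PDL) and 1 × 0.0252 = 0.025 (BI). IO v IANB, IO v BI and PDL v IANB stay below 0.05 under every method tried (largest adjusted p 0.043).

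**Error rate of the ranking.** Simulation with 40 per arm and Pearson tests at 0.05, 400,000 trials per scenario. The success rates are assumptions. Each entry is the chance of declaring at least one difference between arms that are truly equal.

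| Assumed rates (IANB, IO, PDL, BI) | Unadjusted | Unadjusted, only after a significant overall test | Holm over six |
|---|---|---|---|
| 0.675 in all four | 19.1% | 5.0% | 4.1% |
| 0.5, 0.925, 0.5, 0.5 | 13.7% | 13.7% | 4.5% |
| 0.592, 0.925, 0.592, 0.592 | 12.9% | 12.8% | 4.0% |
| 0.4, 0.65, 0.65, 0.65 | 11.8% | 10.6% | 3.0% |
| 0.4, 0.767, 0.767, 0.767 | 12.3% | 12.2% | 3.5% |
| 0.525, 0.825, 0.825, 0.525 | 10.6% | 10.6% | 2.8% |
| 0.4, 0.925, 0.6875, 0.6875 | 4.8% | 4.8% | 1.9% |

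The sixth row is the case in which exactly the two disputed pairs are equal. In the last row only PDL and BI are equal, so only one false claim is possible and no inflation appears.

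**The case against.** The strongest reply is that the loss is marginal and that Holm on Pearson p-values is one choice among several. Hochberg misses by 0.0003, Hommel keeps IO v PDL, and Holm on likelihood-ratio p-values keeps both pairs; the phrase used in the plan does not exclude that form of the test. A closed Pearson test also keeps both, with simulated family-wise error of 4.6 to 5.6% in the scenarios above. This stands. It rules out any flat statement that the two differences are lost, and it is also why the procedure has to be named.

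A second reply is that the family is implied: IANB is called the control and all effect estimates are against it. On that reading Holm keeps BI v IANB. This is plausible, and the fix allows for it. But it does not cover IO v PDL, which the text and the letters assert without calling it exploratory.

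A third reply is that the overall test is highly significant and protects the pairs. With four arms it does so only when all are equal; with three equal arms or two equal pairs the error remains about 10 to 14%. The plan does not state such a two-stage rule either.

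Finally, the document already contains the results, so an adjustment chosen now is chosen with the counts known. That also stands, and any such adjustment should be labelled post hoc.

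**Conclusion.** The omission is real and should be fixed. The stated 0.05 rule does not hold for a ranking over six pairs if those pairs were tested without adjustment, and two of the five claimed differences depend on the choice that is not stated. IO v PDL is the more exposed, because it also falls outside a control-only family. BI v IANB is at risk mainly when all six pairs form the family. The other three differences are secure.

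Three stronger readings are tempting and not supported:

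- A reader might infer that the authors did test the pairs unadjusted. The letters match that, but they also match a closed Pearson test, Holm on likelihood-ratio p-values and Benjamini-Hochberg on Pearson p-values. The documents do not say which was used.
- A reader might infer that IO v PDL and BI v IANB are not real differences. An adjusted p of 0.056 does not show that; the observed gaps of 20 and 25 percentage points are unchanged.
- A reader might infer that Holm over six is the only valid analysis. Other family-wise methods are defensible and some keep both pairs.

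The p-values rest on the Table 2 counts alone. The error rates rest on assumed success rates and on unadjusted testing.

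**What to change.** State the family of comparisons and the pairwise procedure in the Statistical analysis section, and print the six raw and adjusted p-values beside Table 2. Then, according to what was done:

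1. If the pairs were unadjusted, choose one of two forms.
   - All six pairs by Pearson chi-square with Holm to a family-wise 0.05, labelled post hoc. The letters become a, c, bc, ab for IANB, IO, PDL, BI, and BI v IANB is described as sensitive to the adjustment.
   - The three comparisons with the IANB control as the family under Holm (0.000002, 0.007 and 0.025 for IO, PDL and BI), also labelled as chosen after the results. Comparisons among the supplemental techniques, including IO v PDL, are then labelled exploratory.

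   In either form, describe IO v PDL as sensitive to the multiplicity method.
2. If a valid family-wise method was in fact used, name it and print its adjusted p-values; the present letters then stand. If Benjamini-Hochberg was used, say that it controls the false discovery rate only.

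The cost is about two sentences and a column or two of p-values from the existing counts, with no new data. The downside is that, if the pairs were unadjusted, one or two claimed differences become weaker.
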